2.5 Correlative Studies Background: N/A

3. PARTICIPANT SELECTION

3.1 Eligibility Criteria

- 3.1.1 Survivors of mediastinal lymphoma (either Non-Hodgkin's Lymphoma or Hodgkin's Lymphoma) with no active malignancy
- 3.1.2 Prior mediastinal or mantle radiation ≥ 5 years prior to enrollment in the study
- 3.1.3 Age 18-80 years. Patients < 18 years will be excluded since ivabradine has not previously been studied in children. Patients > 80 years will be excluded since patients have to be able to perform a treadmill exercise stress test as part of this study.
- 3.1.4 ECOG performance status: N/A
- 3.1.5 Life expectancy: N/A
- 3.1.6 Participants must have normal organ function as defined below:
 - AST(SGOT)/ALT(SGPT) $\leq 2.5 \times$ institutional upper limit of normal
 - creatinine clearance ≥ 15 mL/min/1.73 m² for participants with creatinine levels above institutional normal.
- 3.1.7 Normal sinus rhythm with resting heart rate ≥ 80 bpm on screening EKG
- 3.1.8 Based on findings in animals, ivabradine may cause fetal harm when administered to a pregnant woman. For this reason, women of child-bearing potential must agree to use highly effective contraception (as described in Appendix A) prior to study entry and for at least 2 weeks after the last dose of ivabradine. Should a woman become pregnant or suspect she is pregnant while she or her partner is participating in this study, she should inform her treating physician immediately.
- 3.1.9 Ability to understand and the willingness to sign a written informed consent document.

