All of the additional autonomic function tests will be performed by [name] in the autonomic function testing laboratory at Faulkner Hospital. Cardiac autonomic function will be assessed using:

1. Deep breathing:

Deep breathing tests cardiac parasympathetic functions. All subjects will be asked to avoid smoking, intake of caffeinated beverages, and strenuous exercise for 12 hours prior to the test. Subjects will be asked to empty their bladder before the test to prevent sympathetic over-activity. They will then be asked to lie quietly in a temperature-controlled room for 20 minutes. A baseline EKG recording will be obtained for one minute to ensure a stable resting heart rate. Subjects will then be asked to inhale and exhale slowly at a rate of 6 breaths/minute and a continuous EKG will be recorded during deep breathing. Respiratory sinus arrhythmia (RSA) amplitude, defined as the difference in heart rate between end expiration and end inspiration, will be recorded for each respiratory cycle and the average RSA will be reported.¹⁹

2. Valsalva maneuver:

Valsalva maneuver evaluates sympathetic adrenergic function using the blood pressure responses and parasympathetic function using the heart rate responses. The Valsalva maneuver consists of forced expiration against resistance with an expiratory pressure during strain of 40 mm Hg for 15 seconds. The maneuver will be performed in the supine position. Patients will be asked to breath into a 10 ml plastic syringe that is connected to a

pressure gauge. They will be asked to take a deep breath and blow into the syringe and keep the pressure at 40 mm Hg for 15 seconds. Subjects will be asked to practice the maneuver to ensure that they can do it correctly prior to the actual measurements. Once they have mastered the maneuver, they will be asked to rest for 3-5 minutes before repeating the maneuver. Heart rate and blood pressure will be recorded non-invasively using the Finapres NOVA system (Finapres Medical Systems, Netherlands). The Valsalva ratio, defined as the maximum heart rate during the maneuver divided by the lowest heart rate obtained within 30 seconds of the peak heart rate, will be measured.¹⁹

3. Tilt Testing:

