Tilt tests predominantly evaluate adrenergic function by applying orthostatic stress. Patients will be placed in the supine position and baseline heart rate and blood pressure will be acquired over 5-10 minutes. The patient will then be tilted up to an angle of 70 degrees over 5-10 seconds. Patients will be closely observed for chest pain, shortness of breath, dizziness, lightheadedness or syncope. If they have no adverse reaction, the heart rate and blood pressure will be assessed every minute for 10 minutes. The patient will then be placed back in the supine position. The increase in heart rate and drop in blood pressure in response to the tilt will be recorded.¹⁹

4. Heart rate variability:

Heart rate variability with low frequency and high frequency oscillations in RR intervals assesses the balance of sympathetic and parasympathetic influences in the heart. Measures of overall heart rate variability and spectral analysis of heart rate variability will be performed with a Matlab based computer system.²⁰

5. Sudomotor testing

Electrochemical skin conductance (ESC) is a new noninvasive test for measurement of sudomotor functions.²¹ ESC correlates with loss of small fiber skin nerves, and it is useful for evaluation of small fiber neuropathy. Measurements using ESC will be performed as described previously.²²

The RSA and Valsalva ratio will be compared to age and gender based normative values (Tables 1 and 2). The cardiovagal composite autonomic severity score (CASS) will be calculated (Table 3). The adrenergic CASS will be calculated (Table 4).¹⁹

Table 1: Normal Values for Deep Breathing Test

Age range (years)	Minimum Normal RSA (beats/min)
10-29	≥ 14
30-39	≥ 12
40-49	≥ 10
50-59	≥ 9
60-69	≥ 7

Table 2: Normal Values for Valsalva Ratio

Age range (years)	Minimum Normal Valsalva Ratio	
	Women	Men
10-29	1.46	1.59
30-39	1.5	1.52
40-49	1.51	1.44
50-59	1.47	1.36
60-69	1.39	1.29

Table 3: Calculation of Cardiovagal Score

Result	Degree of Abnormality	Cardiovagal Score	Definition
Normal		0	
Abnormal	Mild	1	RSA or Valsalva ratio reduced but $\geq 50\%$ of minimal normal values
	Moderate	2	RSA or Valsalva ratio $< 50\%$ of minimal normal values
	Severe	3	Both RSA and Valsalva ratio $< 50\%$ minimal normal values

Table 4: Calculation of Adrenergic Score:

Result	Degree of Abnormality	Adrenergic Score	Definition
Normal	0		

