8.2 IND Agent #2: N/A

8.3 Other Agent #1: N/A

8.4 Other Agent #2: N/A

9. BIOMARKER, CORRELATIVE, AND SPECIAL STUDIES

9.1 Biomarker Studies: N/A

9.2 For IDE Protocols Only: Investigational Device Information: N/A

9.3 Laboratory Correlative Studies: N/A

9.4 Other Agent #2: N/A

10. STUDY CALENDAR

Baseline evaluations/tests are to be conducted within 1 week prior to start of protocol therapy. In the event that the participant's condition is deteriorating, laboratory evaluations should be repeated within 48 hours prior to initiation of therapy.

2 week study evaluations and drug up-titration should be administered within ± 3 days of the protocol-specified date, unless otherwise noted.

Week 6 study evaluations/tests should be conducted within ± 7 days of the protocol-specified date and should be completed prior to termination of study drug.

	Screening visit	Baseline	Week 2	Week 6
Agents:		Ivabradine vs. placebo	Ivabradine or placebo dose titration	Study End
Informed consent	X			
Demographics	X			
Medical history	X		X	X
Physical exam		X	X	X
Concurrent Meds	X	X	X	X
Vital signs	X	X	X	X
Height		X		X
Weight		X		X
Serum chemistry ^a	X			
EKG (as indicated)	X	X	X	X
B-HCG		X ^b		X ^b
Exercise stress test		X		X
24-hr ambulatory Holter monitor		X		X
SF-36 QOL questionnaire		X		X
Sophisticated autonomic function testing ^c		X		X
Adverse event evaluation		X-----X		
a: Review of SGOT [AST], SGPT [ALT], creatinine obtained within the last 12 months. b: Urine pregnancy test (women of childbearing potential). c: For subset of patients randomized to receive autonomic function testing				

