11. MEASUREMENT OF EFFECT

11.1 Antitumor Effect- Solid Tumors: N/A

11.2 Antitumor Effect- Hematologic Tumors: N/A

11.3 Other Response Parameters

Primary end point:

1. Change in HR from baseline to 6 weeks with ivabradine vs. placebo.¹⁷

Secondary end point:

1. Change in exercise duration from baseline to 6 weeks with ivabradine vs. placebo.²³

Exploratory end points:

1. Change in markers of additional cardiac autonomic function: respiratory sinus arrhythmia amplitude, Valsalva ratio, heart rate variability, cardiovagal CASS and adrenergic CASS from baseline to 6 weeks.¹⁹
2. Change in patient reported quality of life (as assessed using then SF 36 questionnaire) from baseline to 6 weeks with ivabradine compared to placebo.²⁴

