13.6 Analysis of Secondary Endpoints

The secondary end-point of this study is the change in exercise duration with ivabradine, compared to placebo, in survivors of lymphoma with mediastinal involvement who were treated with mediastinal/mantle radiation and have a resting HR \geq 80 bpm.

We will calculate the change in exercise duration (from exercise treadmill stress tests) from baseline to 6 weeks for each patient in the study (n=60). An ANCOVA model (for normally distributed data) adjusting for the stratification factors (beta blocking agents [Yes, No], autonomic function testing [Yes, No]) or Quade test adjusting for the stratification factors (beta blocking agents [Yes, No], autonomic function testing [Yes, No]) (for non-normally distributed data) will be implemented to compare the change in exercise duration with ivabradine versus placebo.

We will then repeat the analysis with change in resting HR as an additional independent variable to assess whether change in resting HR affects exercise duration. A p value < 0.05 using a two-sided test will be considered statistically significant.

Exploratory end-points of this study are:

- 1) Change in additional markers of cardiac sympatho-vagal balance with ivabradine, compared to placebo, in survivors of lymphoma with mediastinal involvement who were treated with mediastinal/mantle radiation and have a resting HR \geq 80 bpm.

Since this is an exploratory end-point and due to cost constraints, it will only be conducted in half the patients enrolled in the trial (n=30) and no power calculation has been made. The cardiovagal composite autonomic severity score (CASS) and adrenergic CASS will be calculated at baseline and at 6 weeks (as described in Section 5.3.3) for each patient in this substudy. The change in CASS and adrenergic CASS will then be assessed for each patient. Quade test adjusting for the stratification factors (beta blocking agents [Yes, No], autonomic function testing [Yes, No]) (for ordinal data) will be implemented to compare the change in CASS and adrenergic CASS in patients treated with ivabradine versus placebo. A p value < 0.05 using a two-sided test will be considered statistically significant.

- 2) Change in health related quality of life with with ivabradine, compared to placebo, in survivors of lymphoma with mediastinal involvement who were treated with

mediastinal/mantle radiation and have a resting HR \geq 80 bpm.

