13.7 Reporting and Exclusions

All patients who complete the baseline and 6 week assessments will be included in the analyses.

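### Cardiovagal CASS grade 3 cannot occur under the plan's own Valsalva definition and norms, and ages 70-80 have no norms (exploratory substudy, minor)

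*Combined protocol and SAP*

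**What the plan says.** **Ratio and norms.** In Section 5.3.3 d) the Valsalva ratio is "defined as the maximum heart rate during the maneuver divided by the lowest heart rate obtained within 30 seconds of the peak heart rate". The same section states: "The RSA and Valsalva ratio will be compared to age and gender based normative values (Tables 1 and 2"). Both tables have five age rows, the last being 60-69. Table 1 gives minimum normal RSA by age. Table 2 gives minimum normal Valsalva ratios by age and sex, from 1.29 to 1.59.

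**Scoring.** Table 3 turns the two measures into a cardiovagal score:
- Score 1 (*Mild*): either measure is reduced but still at least half of its norm.
- Score 2 (*Moderate*): either measure is under half of its norm.
- Score 3 (*Severe*): "Both RSA and Valsalva ratio" are under half of their norms.

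**Who is scored.** Section 3.1.3 admits "Age 18-80 years". Sections 13.1 and 13.3 allocate the autonomic substudy by randomization, and footnote c of the Section 10 calendar describes the tests as "For subset of patients randomized to receive autonomic function testing". No age limit is set for the substudy. Section 13.6 says that the two CASS scores "will be calculated at baseline and at 6 weeks (as described in Section 5.3.3) for each patient in this substudy". Section 13.7 adds: "All patients who complete the baseline and 6 week assessments will be included in the analyses".

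**Endpoints and analysis.** Section 11.3 lists change in "respiratory sinus arrhythmia amplitude, Valsalva ratio, heart rate variability, cardiovagal CASS and adrenergic CASS from baseline to 6 weeks". For the substudy, Section 13.6 names only the two CASS scores, compared by a Quade test at two-sided 0.05, and says that no power calculation was made. The general rule in Section 13.3 covers change in the other endpoints by ANCOVA or Quade test, adjusted for the stratification factors, with no baseline value.

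**The concern.** A peak heart rate divided by a trough close to that peak has a floor of 1.0. A cut-off set at half of a norm works for a quantity that can fall to zero, as RSA can. It does not work for a ratio with a floor of 1.0 and norms well below 2.0. If the Valsalva half of Table 3 is empty, the score cannot record its own worst grade, and the Valsalva ratio can do no more than separate score 0 from score 1.

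The age tables raise a second problem. The plan promises a score for every substudy patient, but gives nothing to score patients aged 70-80 against.

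At stake is one of the two scores that Section 13.6 names for exploratory objective (i). It is also the one closest to the hypothesis in Section 2.1 that radiation injures the vagus nerve. If the age gap is left open, the treatment of older patients may be decided after the data are seen.

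**Working it through.** The plan gives no sample size or power figure for this endpoint, so there is none to reproduce. The check uses the ratio definition and Tables 1 to 3 of Section 5.3.3, the age range in Section 3.1.3, and the promise in Section 13.6.

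**1. Floor of the ratio.** Ratio = peak / nearby trough. The trough cannot exceed the peak, so the ratio is at least 1.0. This bound follows from the definition; the plan does not state it as a number.

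**2. Half-norms against the floor.** Half-norm = 0.5 × Table 2 norm. The floor as a share of the norm = 1.0 / norm.

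| Age | Norm, women / men | Half-norm, women / men | 1.0 as % of norm, women / men |
|---|---|---|---|
| 10-29 | 1.46 / 1.59 | 0.730 / 0.795 | 68.5 / 62.9 |
| 30-39 | 1.50 / 1.52 | 0.750 / 0.760 | 66.7 / 65.8 |
| 40-49 | 1.51 / 1.44 | 0.755 / 0.720 | 66.2 / 69.4 |
| 50-59 | 1.47 / 1.36 | 0.735 / 0.680 | 68.0 / 73.5 |
| 60-69 | 1.39 / 1.29 | 0.695 / 0.645 | 71.9 / 77.5 |

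Half-norms run from 0.645 to 0.795, all below 1.0. A completely flat response is still 62.9% to 77.5% of normal. For a ratio of at least 1.0 to fall under half of its norm, the norm would have to exceed 1.0 / 0.5 = 2.0, and the largest is 1.59. Put another way, even the highest half-norm, 0.795, would need a trough 1 / 0.795 = 1.26 times the peak.

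**3. Consequence for the score.** Where a patient meets more than one row of Table 3, take the higher grade. (The table does not say so, but it is the natural reading.) The reachable scores in all ten age-sex cells are then 0, 1 and 2.
- Score 3 needs the Valsalva criterion and never occurs.
- Score 2 needs RSA under half of the Table 1 norm: below 14/2 = 7.0, 12/2 = 6.0, 10/2 = 5.0, 9/2 = 4.5 or 7/2 = 3.5 beats/min, from the youngest row to the oldest.
- RSA 0 with ratio 1.0, no cardiovagal response at all, scores 2 (*Moderate*).
- Normal RSA with ratio 1.0 scores 1 (*Mild*).
- A patient at score 2 stays there whatever the Valsalva ratio does.

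**4. Age coverage.** The eligible ages 18 to 80 span 63 single years. Ages 70 to 80, 11 of them, have neither an RSA nor a Valsalva norm. The plan does not give the share of patients in that range. As an assumption only, with share p among 30 substudy patients, the expected number is 30p and the chance of at least one is 1 − (1 − p)^30:
- p = 5%: 1.5 patients, 0.785
- p = 10%: 3 patients, 0.958
- p = 20%: 6 patients, 0.999

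**The case against.** **The consequence is small.** The endpoint is exploratory, has 30 patients and no power calculation. The missing grade coarsens the scale in the same way in both arms. This stands in full. A reader might infer that the comparison of ivabradine with placebo is biased; nothing in the documents supports that.

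**The origin of Table 3 is not known.** Section 5.3.3 credits the scoring to a cited methods paper that is not available here. Table 3 may be a faithful copy of an instrument with this limitation, or a slip in transcription. This also stands. The documents show that the rule cannot work with its own definition and norms, not how that came about.

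**The continuous measures are already planned.** A reader might infer that RSA amplitude and Valsalva ratio have no planned analysis because Section 13.6 does not name them. That goes too far: Section 11.3 lists them and the general rule in Section 13.3 covers them. What is missing is a baseline term and a clear place beside CASS. Nor does listing autonomic testing as an adjustment factor do harm in the substudy: it is constant there and changes no result.

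**Heart-rate lowering may move the ratio itself.** A reader might infer that ivabradine would raise the Valsalva ratio without any vagal change. The documents do not settle the direction. An equal bpm fall in peak and trough raises the ratio, an equal proportional fall leaves it unchanged, and a proportionally larger fall at the peak lowers it. Section 2.3 describes heart-rate reduction at rest and during exercise, not in either phase of this maneuver. This is a reason for caution with both CASS and the continuous ratio, not a demonstrated bias.

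**The age gap has no documented size.** True. The figures for 5% to 20% are illustrations. The conflict between eligibility, tables and promise does not depend on them.

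**Conclusion.** The point holds and is minor. As written, the Valsalva part of Table 3's under-half criterion is empty in every age-sex cell. Cardiovagal CASS therefore runs 0 to 2 in practice, and total loss of response is graded no worse than *Moderate*. Separately, patients aged 70-80 are eligible, can be randomized to the substudy and are promised a score that Tables 1 to 3 cannot supply; how many there will be is unknown.

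The first conclusion is arithmetic from the plan's own definition and norms. The second assumes that the norm tables are complete as extracted; both show the same five rows, so a lost row is unlikely but cannot be fully excluded. The effect is confined to one exploratory score. The RSA part of Table 3 works as written, and the primary and secondary endpoints and adrenergic CASS are unaffected.

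**What to change.** 1. **Section 5.3.3, Table 3.** Check it against its cited source and reconcile it with Table 2 and the ratio definition. If it departs from the source, correct it. If it does not, state that the cardiovagal score runs 0 to 2 in practice.
2. **Section 13.6.** Make change in continuous RSA amplitude and Valsalva ratio the main cardiovagal comparison, reported alongside CASS. Use ANCOVA adjusted for the baseline value and beta-blocker stratum, or a Quade test with the same covariates if the data are not normal. This needs no age norms, so patients aged 70-80 stay in the analysis.
3. **Ages 70-80.** Say in the same place, before unblinding, how cardiovagal CASS is handled for these patients.

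The cost is wording in two sections, plus a corrected Table 3 if the source differs. Both measures are already collected, so no tests or visits are added. The downside is a few more unadjusted exploratory tests. The Valsalva ratio also needs cautious reading, because lowering heart rate may itself shift it in either direction.

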Abnormal	Mild	1	Valsalva maneuver: Early phase 2 drop in BP: 20-40 mmHg OR Late phase 2 BP does not return to baseline OR Pulse pressure reduction $\leq 50\%$ of baseline OR Systolic pressure recovery time 4-5 seconds
	Moderate	2	Valsalva maneuver: Early phase 2 drop in BP: 20-40 mmHg AND Absent late phase 2 OR Absent phase 4 OR Systolic pressure recovery time 6-9 seconds
	Severe	3	Tilt: SBP reduction ≥ 30 mmHg; MAP reduction ≥ 20 mmHg OR Valsalva maneuver:

			Early phase 2 drop in BP \geq 40 mmHg AND Absent phase 2 AND Absent phase 4 OR Absent phases 2 and 4 systolic pressure recovery time = 10 seconds
	Severe	4	Tilt AND Valsalva maneuver responses in #3

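### Table 4 caps the early phase 2 pressure drop at 40 mmHg for adrenergic scores 1 and 2, so a deeper drop can lower the score and a worsening can count as improvement

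*Combined protocol and SAP*

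**What the plan says.** Section 5.3.3 d) has the adrenergic CASS calculated from Table 4 and cites the quantitative autonomic testing article (reference 19). The Valsalva criteria that matter here are:

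- **Score 1 (mild), any one of:** "Early phase 2 drop in BP: 20-40 mmHg"; "Late phase 2 BP does not return to baseline"; a pulse-pressure criterion; "Systolic pressure recovery time 4-5 seconds".
- **Score 2 (moderate):** the same 20-40 mmHg drop AND absent late phase 2, OR absent phase 4, OR "Systolic pressure recovery time 6-9 seconds". No brackets are given.
- **Score 3 (severe):** a tilt criterion; or a drop of at least 40 mmHg AND absent phase 2 AND absent phase 4; or the line "Absent phases 2 and 4 systolic pressure recovery time = 10 seconds".
- **Score 4:** both the tilt and the Valsalva responses of score 3.

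The table does not say which row applies when several are met, or what to do when none is.

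Section 11.3 lists "cardiovagal CASS and adrenergic CASS from baseline to 6 weeks" among the exploratory endpoints. Section 13.6 adds: "The change in CASS and adrenergic CASS will then be assessed for each patient". It treats the scores as ordinal, compares arms by Quade test in the substudy (n=30, no power calculation), and calls a two-sided p below 0.05 significant.

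**The concern.** A within-patient change on an ordinal scale makes sense only if a worse finding never earns a lower score. Table 4 puts an upper limit on the drop in the two lower rows, and the row that accepts larger drops demands two further abnormalities as well. A patient whose drop passes 40 mmHg without those abnormalities loses the credit that a smaller drop earned.

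At stake is the meaning of a change of one point for such patients. A deepening fall can be recorded as improvement, and a lessening fall as deterioration. With 30 patients split equally between arms (about 15 each) on a 0-4 scale, a few such scores could shift the comparison.

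**Working it through.** No sample size or power figure bears on this point, so the check applies the printed rules to one patient.

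**Notation.** D = early phase 2 drop in mmHg; L = late phase 2 absent; P = phase 4 absent; R = recovery time in seconds. All criteria come from Table 4.

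**Patient.** L true, P false, R = 3, no tilt response. Only D varies.

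**Score 2 under each possible bracketing:**

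1. (20≤D≤40 and L) or P or 6≤R≤9
2. 20≤D≤40 and (L or P or 6≤R≤9)
3. (20≤D≤40 and (L or P)) or 6≤R≤9

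At D = 35 the drop term and L are both true, so all three are met. At D = 45 the drop term is false, P is false and R is outside 6-9. The only true term is L, and each bracketing ties it by AND to the false drop term. None is met.

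**Score 3.** The drop route needs P, which is false. The recovery-time line is not met either: P is false and R is 3. That holds whether the line reads = 10 or ≥ 10, and whether it is joined to the absent phases by AND or OR. There is no tilt response.

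**Score 1.** At D = 45 this is met because an absent late phase 2 does not return pressure to baseline. The pulse-pressure criterion can add nothing above 1.

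| | D = 35 | D = 45 |
|---|---|---|
| Score 1 row | met | met |
| Score 2 row | met | not met |
| Score 3 row | not met | not met |
| Highest row met | 2 | 1 |

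For baseline 35 and week 6 at 45, change = 1 − 2 = −1 (apparent improvement). For baseline 45 and week 6 at 35, change = 2 − 1 = +1 (apparent deterioration).

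**Wider check.** The rules were run over drops of 10 to 60 mmHg, late phase 2 normal, incomplete or absent, phase 4 present or absent, recovery of 2 to 15 s in whole seconds, and tilt yes or no, leaving out the pulse-pressure criterion. Eight readings were used: score 2 bracketed as in 1 or 2 above; the score 3 recovery time joined by AND or OR; and = 10 or ≥ 10. Cases where the score falls while only the drop deepens occur in all eight. Cases where it falls while only recovery time lengthens occur in seven. They vanish if the line should read ≥ 10 with an OR before it and score 2 is bracketed as in 1.

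**After the fix.** If any drop of at least 20 mmHg satisfies the score 1 and 2 drop criterion, D = 45 meets score 2 through L, so both drops score 2 and the change is 0. A criterion with only a lower bound stays met as D rises, so under a highest-row rule a deeper drop cannot lower the score.

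**The case against.** **Quality of the table.** It is visibly damaged in extraction, and the recovery-time line reads as if a connector had dropped out. A reader might infer that a longer recovery time also scores as less abnormal. The documents do not settle this: if = stands for ≥ and an OR is missing, a recovery of 12 s alone scores 3. The objection stands for that line, but the 20-40 mmHg cap is clearly printed in both lower rows.

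**Other apparent faults.** A reader might see gaps at 5-6 s and 9-10 s; in whole seconds the lower bands run 4-5 and 6-9, followed by 10, and no timing resolution is stated. A reader might call the pulse-pressure criterion inverted; it can equally mean a fall to half of baseline or less, so it is at worst ambiguous. A reader might say that clearly abnormal patients are left at 0. With phases normal and recovery 3 s, a 45 mmHg drop does miss every drop band, but the pulse-pressure criterion may still give 1. None of these is established.

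**Expert scoring and blinding.** One laboratory does all the testing, and patients and investigators are blinded (section 8.1.7), so no bias between arms is shown. That stands. It does not repair the definition: section 5.3.3 makes Table 4 the scoring rule, and a laboratory using something else would be departing from the protocol.

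**The cited instrument.** The cap may belong to the source, which is not available here. That stands, and is why checking the source comes before any change to cut-points.

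**Conclusion.** The defect is real and narrow. For a patient with late phase 2 absent, phase 4 present, normal recovery time and no tilt response, a drop that deepens past 40 mmHg lowers the score from 2 to 1. This holds under every AND/OR reading tried and does not depend on the recovery-time or pulse-pressure wording.

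It rests on two assumptions: the highest row met is assigned, which the table does not state, and an absent late phase 2 also counts as failing to return to baseline. Without the second, the score at 45 mmHg would be 1 or 0 depending on pulse pressure, so it would still fall.

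A reader might go on to infer that the direction of any arm difference is uninterpretable. The documents do not support that, because nothing in them shows how many patients would fall in this cell. The effect is limited to one exploratory endpoint in the n=30 substudy. The other autonomic markers in section 11.3 do not use Table 4, and the primary and secondary analyses are untouched.

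**What to change.** Before any test is scored:

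1. Check Table 4 against reference 19 and the original protocol page.
2. Amend the table so that a drop above 40 mmHg that does not meet score 3 still satisfies the drop criterion of the score 1 and 2 rows.
3. Bracket the AND/OR terms in each row and state that the highest row met is assigned.
4. In the same pass, confirm whether the score 3 recovery time is = 10 or ≥ 10 and whether an OR is missing before it, and clarify the pulse-pressure wording.

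The cost is one table amendment and rescoring of traces already recorded; no new test or patient is needed. If the cited source itself carries the cap, the amended table departs from the published instrument, and the protocol should document that departure and the reason for it.
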